### **15.2.3. Unanticipated Adverse Device Effect (UADE)**

An Unanticipated Adverse Device Effect (UADE) is any serious adverse effect on health or safety, any life-threatening problem or death caused by, or associated with a device, if that effect, problem, or death was not previously identified in nature, severity or degree of incidence in the application; or any other unanticipated serious problem associated with a device that relates to the rights, safety, or welfare of subjects.

### **15.2.4. Device complaints**

Those only apply to the approved devices used in the AP device, i.e. the CGM and the insulin pump. Those devices are not being used as they were intended to be used. Effectively, these devices are being used beyond their original intended use when included in a closed-loop. However, their intended output and performance specifications are not being modified: the purpose of the CGM in the closed-loop is still to provide subcutaneous glucose values, while the purpose of the pump in the closed-loop is still to deliver controlled amount of insulin. A device complaint also applies to CONTOUR® NEXT EZ Glucose meter used to calibrate the CGM. It is used per the manufacturer’s instructions.

A complaint means any written, electronic or oral communication that alleges deficiencies related to the identity, quality, durability, reliability, safety, effectiveness, or performance of a device after it is released for distribution. The complaint may or may not be associated with an adverse event.

Should there be any malfunction of the device related to the original intended use for which the device is marketed for, it will be reported to the manufacturer per 21 CFR 803.3. For example, problems with the infusion set (Inset®), or the subcutaneous needle would be independent of the closed-loop trial and will be reported.

Because both Dexcom® and Animas are close partners in the development of an artificial pancreas, they will informally be notified of any other malfunction of their device related to their use in the AP device. This will

be valuable information for further product development of an artificial pancreas.

### 15.2.5. Anticipated adverse events

Each adverse event is graded for its severity from mild to severe as described by [Table 15-1](#)~~Table 9-1~~. This is a measure of intensity only. An adverse event may be severe, but not clinically serious.

**Table 15-1:** Severity of adverse events

Intensity level	Description
Mild	Usually transient, requires no special treatments, and does not interfere with the subject's daily activities
Moderate	Usually causes a low level of inconvenience or concern to the subject and may interfere with daily activities, but is usually ameliorate by simple therapeutic measures.
Severe	Interrupts a subject's usual daily activities and generally requires system drug therapy or other treatment.

Hypoglycemia and hyperglycemia are intrinsic risks and adverse events associated with type 1 diabetes. The level of severity of such events follows a more detailed description as described by [Table 15-2](#)~~Table 9-2~~: it varies from negligible, mild, moderate, severe and very severe. Only hyperglycemia or hypoglycemia that is rated moderate or worse will be documented in a CRF.

**Table 15–2: Levels of hyperglycemia and hypoglycemia as defined by YSI**

Severity	YSI	Clinical symptoms	Description
Hyperglycemia			
Negligible	200<BG<300 mg/dl for <1 hr or BG>300 mg/dl for <1 hr	Asymptomatic	Little or no potential injury, pain or discomfort
Mild	200<BG<300 mg/dl	Mild polydipsia and mild polyuria	Potential of minor injury, pain, or user discomfort
Moderate	BG> 300 mg/dl	Symptoms of ketosis (nausea, polyuria, polydipsia, vomiting) with normal mental status	Potential of non-life threatening injury, pain, or direct or indirect exacerbation of existing non-life threatening condition
Severe	BG>300 mg/dL requiring intravenous fluids to correct	Altered mental state Subject in critical condition	Major injury requiring medical intervention
Very severe	N/A	No heart rate, no blood pressure Subject in critical condition	Potential of death or serious injury
Hypoglycemia			
Negligible	60<BG<70 mg/dL	Asymptomatic or adrenergic/cholinergic symptoms without neurocognitive changes	Little or no potential injury, pain or discomfort
Mild	BG<60 mg/dL Or HMS indicates impending hypoglycemia (<70mg/dL in the next 15 min per CGM measurements)	Asymptomatic or adrenergic / cholinergic symptoms without neurocognitive changes	Potential of minor injury, pain, or user discomfort
Moderate	BG<60 mg/dL	Subject is talking, but early neurocognitive changes such as slow speech, mild affect changes	Non-life threatening injury, pain, or direct or indirect exacerbation of existing non-life threatening condition
Severe	BG<60 mg/dL	Require assistance of another individual due to loss of consciousness, seizure or the inability to administer treatment to self due to neuroglycopenia	Major injury requiring medical intervention
Very Severe	N/A	No heart rate, no blood pressure Subject in critical condition	Potential of death or serious injury

[Table 15–3](#)~~Table 9–3~~ is a list of anticipated adverse events. These will be reported on the CRF found in Appendix 9 of the IDE submission.

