**Table 10–2: Safety action to take in case of hypoglycemic and hyperglycemic events based on YSI values**

CONDITION	ACTION
Hyperglycemia	
Asymptomatic and serum glucose > 250 mg/dL more than 2 hours Or if subject develops nausea, vomiting or abdominal pain	Test the blood for serum ketones. Check the pump, if not running, change pump. If blood ketones exceed 1.0 mmol/L, the study for this subject will be terminated. If a correction bolus needs to be administered by the study staff, it will be administered with a syringe.
Mild polyuria and polydipsia; serum glucose > 250 mg/dL more than 3 hours	If blood ketones were less than 0.6 mmol/L at 2 hours, recheck blood ketones and check the pump. If pump not running or catheter occluded or leaking, change the pump. If blood ketones > 1.0 mmol/L, then the study for this subject will be terminated. If a correction bolus needs to be administered by the study staff, it will be administered with a syringe.
Glucose level $\geq$ 300 mg/dL for more than 1 hour	Investigator will give a manual correction dose bolus administered with a syringe. The trial will be terminated for this subject.
Emesis, but with a normal sensorium and glucose > 350 mg/dL	The study for this subject will be terminated. Intravenous fluids would be given at a rate of 3,000 cc/M2/day. A manual correction dose of a short acting insulin analog would be given. The insulin infusion set would be changed. The subject would remain in the CRC until serum glucose is < 200 mg/dL. Subject will be monitored for at least 2 hours post treatment by study investigator. In case of reoccurring symptoms the subject shall be transferred to the emergency room by paramedics. If a correction bolus needs to be administered by the study staff, it will be administered with a syringe.
Decreased sensorium (sleepy, difficult to arouse) with or without emesis: glucose > 350 mg/dL	The study will be terminated for this subject. The subject will be transferred to the emergency room for evaluation with electrolytes and pH and monitoring for possible further deterioration of neurological status as a decrease sensorium may be indicative of electrolyte and/or pH abnormalities that could lead to respiratory or cardiac depression if not detected and treated appropriately.
Blood glucose >400 mg/dL	The study is terminated for this subject. The investigator will give a manual (with a syringe) correction bolus.

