**Table 15–3: Anticipated Adverse Events**

Adverse event	Description
Hypoglycemia	Refer to details in Table 9-2. Only report if moderate or worse.
Hyperglycemia	Refer to details in Table 9-2. Only report if moderate or worse.
Skin irritation	From sensor wear or insulin pump infusion set. Only considered an AE if the irritation is severe or meets definition of SAE
Bruising at the side of insertion of CGM, infusion set, IV	Only considered an AE if bruising is severe or meets definition of SAE.
Infection at the side of insertion of CGM, infusion set, IV	Only considered an AE if infection is severe or meets definition of SAE.
Pain or bleeding at the side of insertion of CGM or infusion set	Only considered an AE if pain or bleeding is severe or meets definition of SAE.
Infection at side of finger stick	Only considered an AE if infection is severe or meets definition of SAE
Glucose sensor break	Glucose sensor rupture leaves a small portion of the sensor under the skin that may cause redness, swelling or pain at the insertion site

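### Table 15-2 gives no grade to asymptomatic glucose above 300 mg/dL lasting an hour or more and calls a short asymptomatic value above 400 Negligible, so session-ending hyperglycaemia can fall outside the graded adverse event account

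*Combined protocol and SAP*

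**What the plan says.** Table 15-2 (section 15.2.5) defines the hyperglycaemia grades:

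- Negligible, the only grade labelled asymptomatic: "200<BG<300 mg/dl for <1 hr or BG>300 mg/dl for <1 hr".
- Mild: between 200 and 300 mg/dL, with "Mild polydipsia and mild polyuria".
- Moderate: above 300 mg/dL, with "Symptoms of ketosis (nausea, polyuria, polydipsia, vomiting) with normal mental status".
- Severe: "BG>300 mg/dL requiring intravenous fluids to correct", with altered mental state.
- Very severe: absent heart rate and blood pressure, with no glucose value given.

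Section 15.2.5 sets the recording level: "Only hyperglycemia or hypoglycemia that is rated moderate or worse will be documented in a CRF". Table 15-3 repeats it for the hyperglycaemia entry: "Only report if moderate or worse".

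Table 10-2 (section 10.4.2.3) sets the actions. Once glucose has stayed at or above 300 mg/dL beyond 1 hour, the stated action is: "Investigator will give a manual correction dose bolus administered with a syringe. The trial will be terminated for this subject". Above 400 mg/dL, the stated action is: "The study is terminated for this subject. The investigator will give a manual (with a syringe) correction bolus". Neither row asks for symptoms. In section 11.4.1 the visit ends at YSI above 400 mg/dL only if the investigator chooses to give a correction bolus.

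Four other places bear on recording. Section 11.4.1 puts every termination, with its reason, on the CRF. Section 10.4.2.3 puts every outside intervention there too. Table 16-3 makes time above 400 mg/dL, and time at or above 300 mg/dL lasting more than 1 hour, secondary endpoints by CGM and YSI. Section 15.3 says that all adverse events are entered on the CRF, with intensity taken from Table 15-1.

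**The concern.** The grading table and the action table do not cover the same states. A subject without symptoms whose glucose stays above 300 mg/dL for over an hour receives an insulin bolus by syringe and leaves the trial session, yet no row of the grading table describes that subject. A subject without symptoms who briefly exceeds 400 mg/dL has a grade, but it is the lowest one.

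The recording rule turns this into a reporting matter. If hyperglycaemia is reported as an adverse event only from Moderate upwards, and Moderate needs symptoms of ketosis, then no asymptomatic hyperglycaemia of any height or duration can be reported by that route. Section 2.2 refers to this table for the severity levels behind the secondary endpoints, section 16.4.1 includes a review of all adverse events, and section 15.1 sends anticipated adverse events to the IRB and FDA. An excursion that the closed loop failed to contain, and that ended the session, could be missing from that account or be handled differently from one subject to the next.

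**Working it through.** No sample size or error rate is involved, and the plan states no figure to reproduce. The check codes each hyperglycaemia row of Table 15-2 as a rule and compares the result with the two symptom-free termination rows of Table 10-2.

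Rules from Table 15-2, with G the YSI glucose in mg/dL and t the duration in hours:

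- Negligible: asymptomatic, t < 1, and either 200 < G < 300 or G > 300.
- Mild: 200 < G < 300 with mild thirst and urination.
- Moderate: G > 300 with symptoms of ketosis.
- Severe: G > 300 with altered mental state and intravenous fluids.

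Rule from Table 10-2: the session ends if (G ≥ 300 and t > 1) or G > 400.

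Results for a subject without symptoms:

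| G (mg/dL) | t = 0.5 h | t = 1.0 h | t = 1.5 h |
|---|---|---|---|
| 250 | Negligible | no grade | no grade |
| 300 | no grade | no grade | no grade, session ends |
| 320 or 380 | Negligible | no grade | no grade, session ends |
| 420 | Negligible, session ends | no grade, session ends | no grade, session ends |

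Four things follow.

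1. Asymptomatic glucose above 300 mg/dL has no grade from 1 h on. Beyond 1 h, Table 10-2 ends the session in exactly that state.
2. Asymptomatic glucose above 400 mg/dL for under 1 h does have a grade. The second limb of the Negligible row has no upper limit, so a value that ends the session under Table 10-2 is Negligible.
3. A value of exactly 300 mg/dL has no grade at any duration, because both limbs use strict inequalities. The Mild and Moderate rows do the same, so symptoms do not help.
4. Asymptomatic values between 200 and 300 mg/dL for 1 h or more also have no grade. These two symptom-free rows do not end the session there, so this gap is one of completeness.

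For subjects with symptoms, 250 mg/dL with mild thirst and urination is Mild, and 320 mg/dL or more with ketosis symptoms is Moderate. At 320 mg/dL or more with only mild thirst and urination there is no grade on a strict reading. The Moderate row lists both among its ketosis symptoms, so a rater could equally choose Moderate.

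No asymptomatic cell reaches Moderate, so none meets the recording level of section 15.2.5 and Table 15-3.

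The hypoglycaemia half of Table 15-2 lacks this duration gap: an asymptomatic value below 60 mg/dL is Mild however long it lasts.

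**The case against.** The strongest reply is that these events are captured elsewhere. The termination and its reason go on the CRF (section 11.4.1), as does the correction bolus (section 10.4.2.3). Table 16-3 summarises time above 400 mg/dL and sustained time at or above 300 mg/dL, and the second measure is close to the state that Table 15-2 leaves ungraded. Section 16.4.1 also reviews the need for outside intervention. All of this stands. A reader might infer from the grading gap that the worst excursions would go unrecorded; the documents do not support that. What is missing is the grade and a clear adverse event entry.

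A second reply is that section 15.3 sends all adverse events to the CRF with intensity by Table 15-1, which could serve as a fallback. But section 15.2.5 sends hyperglycaemia to Table 15-2 and restricts what is documented, and nothing names Table 15-1 as the default where Table 15-2 has no row. The two sections conflict.

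A third reply is that grade and termination measure different things. Table 15-2 grades by symptoms and potential injury, whereas termination is an operational rule. The hypoglycaemia side shows this: asymptomatic glucose below 60 mg/dL without an HMS warning ends the session, yet is Mild. That stands too. It is a good reason not to insist that every session-ending event be Moderate or worse. It does not explain why some states have no grade at all.

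**Conclusion.** The point holds as a gap in classification and reporting. Asymptomatic YSI glucose above 300 mg/dL for 1 h or more has no grade, and asymptomatic glucose above 400 mg/dL for under 1 h is Negligible. Table 10-2 ends the session above 400 mg/dL, and at 300 mg/dL or more once it has lasted over 1 hour. Under section 15.2.5 and Table 15-3 such events would be absent from the graded adverse event account. Section 15.3 conflicts with that restriction, and Table 10-2 and section 11.4.1 differ on whether a value above 400 mg/dL ends the session by itself.

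The size cannot be estimated. One affected subject would be 1/20 = 5% to 1/12 = 8.3% of the sample, but the documents give no rate for asymptomatic glucose above 300 mg/dL for an hour, so the count may be small or zero. A reader might infer that such events are common from Table 3-1, where glucose in the earlier study was above 180 mg/dL for 28% of the dinner window and 35% of the breakfast window. Those figures do not show how often 300 mg/dL was exceeded. The summary of that study reports no values reaching a level that could affect safety, and the plan expects the inhaled dose to lower the peaks.

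The conclusion rests on reading the rows of Table 15-2 as written, with value, duration and symptoms all required. The primary time-in-range measures do not use these grades.

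**What to change.** Reconcile Table 15-2, Table 15-3, Table 10-2 and sections 11.4.1, 15.2.5 and 15.3:

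- Redraw the hyperglycaemia rows of Table 15-2 so that each combination of value, duration and symptoms maps to exactly one grade, including exactly 300 mg/dL and asymptomatic values lasting 1 h or more.
- State one adverse event recording route for every glycaemic event that ends a session, and list those events in the safety summary whatever their grade.
- Say whether Table 15-1 or Table 15-2 governs hyperglycaemia, so that sections 15.2.5 and 15.3 agree.
- Align Table 10-2 and section 11.4.1 on values above 400 mg/dL.

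Which grade each state receives, and any treatment or termination threshold, is for the sponsor to decide. The main cost is one table and one sentence on recording, with short wording changes where the sections disagree. No new measurements are needed, and there may be a few more adverse event entries.

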**Table 15–3: Anticipated Adverse Events**

Adverse event	Description
Hypoglycemia	Refer to details in Table 9-2. Only report if moderate or worse.
Hyperglycemia	Refer to details in Table 9-2. Only report if moderate or worse.
Skin irritation	From sensor wear or insulin pump infusion set. Only considered an AE if the irritation is severe or meets definition of SAE
Bruising at the side of insertion of CGM, infusion set, IV	Only considered an AE if bruising is severe or meets definition of SAE.
Infection at the side of insertion of CGM, infusion set, IV	Only considered an AE if infection is severe or meets definition of SAE.
Pain or bleeding at the side of insertion of CGM or infusion set	Only considered an AE if pain or bleeding is severe or meets definition of SAE.
Infection at side of finger stick	Only considered an AE if infection is severe or meets definition of SAE
Glucose sensor break	Glucose sensor rupture leaves a small portion of the sensor under the skin that may cause redness, swelling or pain at the insertion site

### **15.3. Adverse event reporting and protocol monitoring**

The first concern will be the safety of the subject, and appropriate medical intervention will be made to address any adverse event.

All adverse events will be recorded on the CRF (Appendix 9 of the IDE), including those that may have occurred during the outpatient phase of the trial (the investigator will elicit reports of adverse events from the subject).

In case of a Serious Adverse Event, the study will be put on hold until a thorough investigation is performed and documented to determine the root cause of the event. Based on the results, the Sponsor/investigator will determine appropriate action, including changes to the protocol or termination of the study, and notify the appropriate regulatory authorities if required.

*Intensity:* The intensity of the adverse event will be recorded based on [Table 15–1](#)~~Table 9–1~~. The term severe is a measure of intensity, not clinical severity. A severe AE is not necessarily a serious AE. For example, itching for several days may be rated as severe, but may not be clinically serious.

*Causality:* The study investigator will assess the relationship of any adverse event to be related or unrelated to participation in the protocol by determining if

there is a reasonable possibility that the adverse event may have been caused by the study device or study procedures.

*Outcome:* Adverse events that continue after the participant's discontinuation or completion of the study will be followed until their medical outcome is determined or until no further change in the condition is expected.

## 16. DATA ANALYSIS

### 16.1. Overview

This section presents the statistical analysis that will be used to evaluate the primary and secondary end-points of the non-randomized feasibility study. These are based on CGM data. The primary endpoints consist in measuring the percentage of time the glucose level of the subject is in the safe zone [80-140] mg/dL, including overnight and excluding 5 hours postprandial and during exercises and 3 hours post-exercise. The expected glucose levels during those periods are:

- 5 hours postprandial: [70-180] mg/dL
- During exercise and for 3 hours after exercise: [70-150] mg/dL

The secondary endpoints consist in measuring the glucose extremes and the need for outside intervention to address hypoglycemia and hyperglycemia. The restoration of glucose level to a safe range, i.e. within [80-140] mg/dL after the two unannounced meals and the exercise without the need of intervention to address hypo- or hyperglycemia, i.e. no physician override to inject insulin or give carbohydrate to the subject, will be considered a successful outcome.

If outside intervention is the result of notification from the Health Monitoring System algorithm (HMS), then it will be considered a successful outcome as well.

There is no control group since the patient is his/her own control. In addition, a more refined data analysis will be performed as discussed below.

### 16.2. Control Variability Grid Analysis

The overall performance of the control algorithm will be visualized via the Control Variability Grid Analysis (CVGA), which is built on a mix/max plot of glucose values. For each subject, a point is plotted with the X-coordinate defined as the minimum blood glucose and the Y-coordinate defined as the maximum blood glucose level for an observation period. In this trial, the

observation period is the 24-hour closed-loop including the unannounced meals and exercise segments.

In order to reject sensor errors, the minimum glucose level is set at the 2.5th percentile and the maximum glucose level is set at the 97.5th percentile of the glucose level distribution, in other words, the Y-X coordinate difference corresponds to the 95% spread of the observed distribution. The plot is then split into zones defined by their X and Y coordinate ranges as follows. The zones are color coded to facilitate the visual interpretation of the results:

- the green zone is safe and acceptable,
- the orange/yellow zone is not desirable, and
- the red-zone would be considered failure of the safety of the Artificial Pancreas device.

Numerically, the information contained in the CVGA, can be described as the percentages within each zone. For example, in [Figure 3-1](#) which present the preliminary results of IDE G090129, there were 40% of the data points in zone A, 60% in zone B and 0% in zones C or D. In other words, the CVGA can be interpreted as a display of event-based clinical characteristics of the control algorithm. [Table 16-1](#) shows the interpretation of the various zones in the CVGA representation.

**Table 16-1: Interpretation of the CVGA zones**

Zone ID	Clinical impact	X coordinate	Y coordinate
A-zone	Accurate control	110-90 mg/dL	110-180 mg/dL
Lower B	Benign deviations from hypoglycemia	90-70 mg/dL	110-180 mg/dL
B-zone	Benign control deviation	90-70 mg/dL	180-300 mg/dL
Upper B	Benign deviation into hyperglycemia	110-90 mg/dL	180-300 mg/dL
Lower C	Over-correction of hypoglycemia	<70 mg/dL	110-180 mg/dL
Upper C	Over-correction of hypoglycemia	110-90 mg/dL	>300 mg/dL
Lower D	Failure to deal with hypoglycemia	<70 mg/dL	180-300 mg/dL
Upper D	Failure to deal with hyperglycemia	90-70 mg/dL	>300 mg/dL
E-zone	Erroneous control	<70 mg/dL	>300 mg/dL

